### 5.11.3 Hypersensitivity Laboratory Measurements

Hypersensitivity labs header data will be listed only. Analysis of the lab results themselves will not be completed as part of this analysis plan and will be outlined in a separate document.

### 5.11.4 Laboratory Data

Descriptive statistics of the observed values and change from baseline (continuous data) will be presented by treatment group and visit for each hematology, urinalysis and serum chemistry parameter. Each measurement (continuous data) will be classed as below, within, or above normal range, based on ranges supplied by the laboratory used. Shift tables in relation to the normal range from baseline to each follow-up visit will be presented.

A listing of any abnormal laboratory measurements recorded throughout the study will be presented.

Laboratory data will be presented in SI units.

### 5.11.5 Vital Signs

Descriptive statistics for observed values and changes from baseline in the following vital signs will be presented by treatment group and visit:

- Systolic blood pressure (mmHg)
- Diastolic blood pressure (mmHg)
- Pulse rate (bpm)
- Respiration rate (breath / min)
- Body temperature (degrees Celsius)
- Body weight (kg)

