### 2.2.1. Summary of Nonclinical Data

The cynomolgus monkey and Sprague Dawley rat were selected as the species for safety assessment. Due to the homology of the SCAP mRNA target sequence with humans, cynomolgus monkeys (and not rat) are pharmacologically responsive to LY3885125 and allow assessment of adverse effects related to the intended pharmacologic activity. This species selection strategy allows for evaluation of off-target and oligonucleotide-related class effects in both species and potential exaggerated pharmacology in monkeys. This is an accepted approach for the safety evaluation of oligonucleotides (Kornbrust et al. 2013; FDA/CDER Onpatro NDA 210922).

A single-dose monkey study CCI was conducted to assess cytokine and complement activation after a single administration of LY3885125. Administration of CCI or CCI mg/kg LY3885125

to male cynomolgus monkeys (*Macaca fascicularis*) once via SC injection resulted in no LY3885125-related effects on mean body weight, clinical observations, coagulation or clinical chemistry parameters, or effects on cytokine (CCI) and complement (CCI) parameters.

A standalone cardiovascular study was conducted to evaluate the potential cardiovascular effects of LY3885125 in instrumented male cynomolgus monkeys (CCI). CCI male cynomolgus monkeys were administered by SC injection single doses of control CCI or CCI mg LY3885125/kg via SC injection (1 males per group).

No LY3885125-related qualitative electrocardiogram (ECG) abnormalities or quantitative changes in PR interval, QRS duration, QT interval, or individual heart rate-adjusted QT (QTc) interval were noted up to CCI postdose following administration of CCI.

Monkeys administered CCI LY3885125 were noted to have a transient increase in heart rate (of up to CCI bpm) from CCI hours postdose, which resolved by CCI postdose; a transient increase in systolic (CCI), diastolic (CCI), and mean arterial blood pressure CCI from CCI postdose, which resolved by CCI; and an increase in body temperature (CCI) from CCI postdose, which resolved by CCI postdose. No heart rate, blood pressure, or body temperature changes were noted in monkeys administered CCI.

No LY3885125-related changes in arterial pulse pressure or dP/dtmax (maximal rate of rise in pressure), or changes in locomotor activity were noted up to CCI following administration of CCI.

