**Table 2.2 Important Potential Safety Risks with LY3885125**

Potential Risk of Clinical Significance	Summary of Data/Rationale for Risk	Mitigation/Monitoring Strategy
Hypersensitivity or allergic reactions	Not specific to LY3885125. Oligonucleotide therapies, both marketed and those in development, have been associated with hypersensitivity events.	Monitor for hypersensitivity reactions in participants. Assess spontaneously reported adverse events for their likelihood to represent hypersensitivity reactions. Once identified, investigative site personnel will collect additional information to characterize the type of reaction using standardized forms. Qualified staff will have received training and have access to supportive measures to manage the reactions.
Injection-site reactions	Not specific to LY3885125. As this molecule is an injectable therapeutic, there is the potential risk of localized injection-site reactions.	Qualified staff will have received training and have access to supportive measures to manage the reactions.
CCI [REDACTED]	Specific to LY3885125. CCI [REDACTED] [REDACTED] Further information is provided in the IB.	Vital signs and ECG will be recorded across multiple scheduled time points following single and multiple doses.
CCI [REDACTED]	CCI [REDACTED] [REDACTED] CCI [REDACTED]	CCI [REDACTED] [REDACTED]

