## 5.2.8 Unscheduled Visits

Only scheduled post-baseline laboratory and vital signs values will be tabulated unless otherwise stated. Post-baseline repeat / unscheduled assessments will be included in all listings in the relevant appendices to the CSR.

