### 5.3 Conventions

All data listings, summaries, figures, and statistical analyses will be generated using SAS version 9.4 or higher.

Part A summaries will be presented by treatment group. Treatment group labels for Part A TFLs will be displayed as follows, with the addition of “Part A Overall (N=XX)”, when appropriate:

QMD Ref: Worldwide-TMP-ST-054-1.0_Effective: 12Aug2022	Governing QMD: Worldwide-SOP-ST-026
Confidentiality Statement This document is the property of Worldwide Clinical Trials Inc. and may not be duplicated, copied, altered or removed from company without prior approval from Worldwide Quality Assurance or in compliance with Worldwide Standard Operating Procedures.	

Worldwide Clinical Trials Controlled Quality Management Document		
 WORLDWIDE CLINICAL TRIALS	Sponsor:	Eli Lilly and Company
	Protocol Number:	J4N-MC-YFAA
STATISTICAL ANALYSIS PLAN		

LY3885125 CCI (N=XX)	LY3885125 CCI (N=XX)	LY3885125 CCI (N=XX)	LY3885125 CCI (N=XX)	LY3885125 CCI (N=XX)	Pooled LY3885125 (N=XX)	Pooled Placebo (N=XX)
-----------------------------------	-----------------------------------	-----------------------------------	-----------------------------------	-----------------------------------	-------------------------------	-----------------------------

Part A listings will be sorted in the following order: treatment group, participant, parameter, and visit unless otherwise stated. All data will be listed, participants who were not randomized will be displayed after the randomized treatment groups/ arms.

Continuous variables will be summarized by the number of non-missing observations, mean, median, standard deviation, and minimum and maximum.

Categorical variables will be summarized by presenting the frequency and percent. Percentages will be based on the number of participants in the column header unless otherwise specified in the footnote. For each variable, all categories will be shown. Zero frequencies (but not the percent) within a category will be presented.

Means, medians and percentiles will be displayed to one more decimal place than the data, dispersion statistics (e.g., standard deviation) will have two more decimal places, and the minimum and maximum will be displayed to the same number of decimal places as reported in the raw data. Percentages will be displayed with one decimal place.

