### 5.11.6 Electrocardiogram Data

Descriptive statistics for observed values and changes from baseline in the following ECG variables will be tabulated at each follow-up:

- Heart rate (bpm)
- PR interval (ms)
- QRS complex (ms)
- QT interval (ms)
- QTc interval (ms)
- QTcF interval (ms) [Fridericia's formula]
- QTcB interval (ms) [Bazett's formula]
- RR interval (ms)

QMD Ref: Worldwide-TMP-ST-054-1.0_Effective: 12Aug2022	Governing QMD: Worldwide-SOP-ST-026
Confidentiality Statement This document is the property of Worldwide Clinical Trials Inc. and may not be duplicated, copied, altered or removed from company without prior approval from Worldwide Quality Assurance or in compliance with Worldwide Standard Operating Procedures.	

Worldwide Clinical Trials Controlled Quality Management Document		
 WORLDWIDE CLINICAL TRIALS	Sponsor:	Eli Lilly and Company
	Protocol Number:	J4N-MC-YFAA
STATISTICAL ANALYSIS PLAN		

Number and percentage of subjects that meet each of the following categories will be presented:

- Largest postdose assessment of QTcF > 450
- Largest postdose assessment of QTcF > 480
- Largest postdose assessment of QTcF > 500
- Largest QTcF change from baseline > 30
- Largest QTcF change from baseline >60

Shift tables in relation to the overall interpretation (Normal; Abnormal Not Clinically Significant [NCS], and Abnormal Clinically Significant [CS]) from baseline to each follow-up visit will be presented.

The relationship between plasma PK concentrations of LY3885125 and  $\Delta$ QTcF will be quantified using a linear mixed-effects modelling approach. The model will have  $\Delta$ QTcF as the dependent variable, plasma PK concentrations of LY3885125 as the explanatory variate (0 for placebo), baseline QTcF as an additional covariate, study treatment (active = 1 or placebo = 0) and time (i.e., post-dose time point: categorical) as fixed effects, and random effects on intercept and slope per participant. In all calculations, concentrations in participants who received placebo will be set to zero. LY3885125 plasma PK concentrations below the quantifiable limit at pre-dose will be set to zero and after dosing will be set to 1/2 the lower limit of quantitation in the concentration-QTc analysis.

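### Pulse and blood pressure, the measures that rose transiently in monkeys, get no count of participants by largest post-dose rise, no stated same-day time points and no unscheduled readings in their table.

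*SAP*

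**What the plan says.** For vital signs, SAP 5.11.5 says: "Descriptive statistics for observed values and changes from baseline in the following vital signs will be presented by treatment group and visit". SAP 5.3 defines the summary: "Continuous variables will be summarized by the number of non-missing observations, mean, median, standard deviation, and minimum and maximum". SAP 5.2.8 limits the table: "Only scheduled post-baseline laboratory and vital signs values will be tabulated unless otherwise stated". Repeat and unscheduled readings appear only in the listings. The output list in SAP section 10 has one vital-sign table (14.3.4.1) and one listing of individual values (16.2.8.6).

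For the ECG, SAP 5.11.6 counts participants by largest post-dose QTcF (three levels) and by largest change (two levels), for example "Largest QTcF change from baseline > 30". ECG heart rate has no such count. Laboratory data get normal-range shift tables and an abnormal-value listing (SAP 5.11.4).

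Protocol 2.2.1 reports no drug-related change in PR, QRS, QT or QTc in the monkey cardiovascular study. It does say that animals at a redacted dose "were noted to have a transient increase in heart rate", with transient rises in systolic, diastolic and mean arterial pressure. All of these resolved. For a risk described as specific to LY3885125, whose name is redacted, Protocol Table 2.2 gives this monitoring: "Vital signs and ECG will be recorded across multiple scheduled time points following single and multiple doses".

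**The concern.** Safety is the primary objective of Part A, and the nonclinical cardiovascular signal lay in heart rate and blood pressure. Participant-level peak counts are planned for the interval that showed no signal and not for the measures that did.

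For an effect lasting hours, a safety reader wants to know how many participants rose at each dose, and how many did so on placebo. A maximum per visit does not answer that. It comes from one participant, and maxima at different visits may or may not come from the same person. Someone would have to count by hand from the listing, with limits chosen after seeing the data.

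The time axis adds to the problem. PK concentrations are summarised at each nominal sample time (SAP 5.3), and the concentration-QTc model uses post-dose time point (SAP 5.11.6). Vital signs are summarised by visit only. A high reading that prompts an unscheduled repeat leaves the repeat out of the table.

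**Working it through.** **Group sizes.** I take the randomisation ratios in Protocol 4.1.1 as cohort sizes: 2 × (6+2) + 3 × (9+2) + (10+9) = 16 + 33 + 19 = 68. This reproduces the approximately 68 completers in Protocol 9.5. The SAP says Cohort 6 was not enrolled. Cohorts 1 to 5 therefore give 2 × 6 + 3 × 9 = 39 active and 5 × 2 = 10 pooled placebo, 49 in all.

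**Assumptions.** The documents give no SD, limit or incidence for vital signs, and the size and timing of the monkey rise are redacted. The SDs, rises, number of readings, correlation and the 20 bpm limit below are therefore illustrative.

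**What the planned statistics show at one reading.**
- Mean: one participant rising 20 bpm moves it by 20/6 = 3.3, 20/9 = 2.2 or 20/39 = 0.5 bpm.
- Maximum change (SD 8, simulated medians): in a group of 9 it is 11.6 with nobody affected, 20.4 with one participant rising 20 bpm and 24.4 with two. In the pooled active column of 39 it is 16.9 with nobody affected and 21.5 with one.

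The maximum does reveal a large rise in a dose group, less clearly in the pooled column. It hardly separates one affected participant from two.

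**Maximum against count.** Simulation of 9 participants, SD 8, six readings with within-participant correlation 0.5, and a 25 bpm rise at two of the six readings in each affected participant:

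| Affected of 9 | Median largest change (bpm) | Expected number reaching 20 bpm |
|---|---|---|
| 1 | 28 | 1.1 |
| 2 | 32 | 2.0 |
| 3 | 34 | 2.8 |

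The count tracks the number affected; the maximum barely moves.

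**Chance crossings.** With nobody affected and one reading, P(at least one of 9 reaches 20 bpm) = 1 − Φ(20/SD)^9, which is 5% at SD 8 and 19% at SD 10. Over six readings with correlation 0.5, simulation gives about 24% and 60%. If the readings were independent it would be 1 − Φ(20/SD)^54 = 29% and 71%.

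The 24% and 60% imply a per-participant probability of 1 − 0.76^(1/9) = 0.030 and 1 − 0.40^(1/9) = 0.097. About 0.3 to 1.0 of the 10 placebo participants would then be expected to cross. That is the background against which an active count has to be read.

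**The case against.** The strongest reply is that little is lost. The minimum and maximum are planned for observed values and for changes, so the largest scheduled rise is printed for each group and visit. All readings, including unscheduled ones, are listed, and with 6 or 9 active participants per dose a count by hand is feasible. A vital-sign change judged clinically significant is an adverse event (Protocol 10.3.1) and is tabulated as such. Protocol 9.3.5 plans descriptive summaries for vital signs and allows further analysis if the data warrant it. QT has its own analysis because Protocol 9.3.6 asks for one under ICH E14.

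Much of this stands, and it rules out stronger readings that a reader might infer:
- That only means are planned, so a rise would be averaged away. SAP 5.3 prints the maximum too.
- That a count would detect a rise more often. At a single reading, at least one participant reaching 20 bpm is the same event as the maximum reaching 20. Setting a count against a confidence interval for the mean difference proves nothing, because Protocol 9.3.5 plans no safety comparisons.
- That the monkey data point to an effect in a minority. Protocol 2.2.1 does not say how many animals rose.
- That same-day readings will be averaged. The SAP does not say so, the vital-sign times in the Schedule of Activities are redacted, and the table shells are a separate document. The supported point is that the wording leaves this open.
- That the Table 2.2 risk is the heart-rate and blood-pressure finding. This is plausible, but the name is redacted.

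What the reply leaves unanswered is the number affected. Adverse-event reporting depends on the investigator's judgement, and limits chosen while reading the listing are post hoc.

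**Conclusion.** The point holds as a gap in presentation that should be closed before database lock. It does not invalidate the safety evaluation. The plan will show that at least one participant had a large rise at a scheduled reading. It will not show how many did, or how that number compares with pooled placebo, and it does not fix the time point within a day.

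In the illustration, going from one to three affected participants of 9 changes the largest value by about 6 bpm (28 to 34), while the expected count goes from 1.1 to 2.8. These figures rest on assumed SD, rise, correlation and limit. The absence of a count, the by-visit wording and the exclusion of unscheduled readings come directly from the SAP.

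**What to change.** In SAP 5.11.5:
- Tabulate pulse, systolic and diastolic pressure by nominal post-dose time point.
- Add one descriptive table of the number and percent of participants whose largest post-dose increase exceeds stated limits, by dose, pooled active and pooled placebo. Fix the limits before database lock. They are reporting limits only; the 20 bpm used above is illustrative.
- Show the table on scheduled readings, and again with unscheduled readings included.

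Add the table to SAP section 10. If the database is already locked, SAP section 5 provides for an addendum, and the limits should then be labelled as chosen after lock.

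The cost is one SAP paragraph and one small table from data already collected, in a format that the SAP already uses for QTcF. The downside is that some participants will cross the limits by chance, so a footnote should say that the counts are to be read against pooled placebo.

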### 5.11.6 Electrocardiogram Data

Descriptive statistics for observed values and changes from baseline in the following ECG variables will be tabulated at each follow-up:

- Heart rate (bpm)
- PR interval (ms)
- QRS complex (ms)
- QT interval (ms)
- QTc interval (ms)
- QTcF interval (ms) [Fridericia's formula]
- QTcB interval (ms) [Bazett's formula]
- RR interval (ms)

QMD Ref: Worldwide-TMP-ST-054-1.0_Effective: 12Aug2022	Governing QMD: Worldwide-SOP-ST-026
Confidentiality Statement This document is the property of Worldwide Clinical Trials Inc. and may not be duplicated, copied, altered or removed from company without prior approval from Worldwide Quality Assurance or in compliance with Worldwide Standard Operating Procedures.	

Worldwide Clinical Trials Controlled Quality Management Document		
 WORLDWIDE CLINICAL TRIALS	Sponsor:	Eli Lilly and Company
	Protocol Number:	J4N-MC-YFAA
STATISTICAL ANALYSIS PLAN		

Number and percentage of subjects that meet each of the following categories will be presented:

- Largest postdose assessment of QTcF > 450
- Largest postdose assessment of QTcF > 480
- Largest postdose assessment of QTcF > 500
- Largest QTcF change from baseline > 30
- Largest QTcF change from baseline >60

Shift tables in relation to the overall interpretation (Normal; Abnormal Not Clinically Significant [NCS], and Abnormal Clinically Significant [CS]) from baseline to each follow-up visit will be presented.

The relationship between plasma PK concentrations of LY3885125 and  $\Delta$ QTcF will be quantified using a linear mixed-effects modelling approach. The model will have  $\Delta$ QTcF as the dependent variable, plasma PK concentrations of LY3885125 as the explanatory variate (0 for placebo), baseline QTcF as an additional covariate, study treatment (active = 1 or placebo = 0) and time (i.e., post-dose time point: categorical) as fixed effects, and random effects on intercept and slope per participant. In all calculations, concentrations in participants who received placebo will be set to zero. LY3885125 plasma PK concentrations below the quantifiable limit at pre-dose will be set to zero and after dosing will be set to 1/2 the lower limit of quantitation in the concentration-QTc analysis.

An unstructured covariance matrix will be specified for the random effects. If convergence cannot be achieved even after appropriate rescaling of the concentrations, the random effect on the slope and intercept will be dropped, in this order, until convergence is achieved. The degrees of freedom (df) estimates will be determined by the Kenward-Roger method. From the model, the slope (i.e., the regression parameter for the concentration) and the treatment effect-specific intercept (defined as the difference between active and placebo) will be estimated together with the 2-sided 90% CI. The estimates for the time effects will be reported with standard error (SE).

The following SAS codes can be used to conduct the LME model in the example:

```
proc mixed data=PKQTc method=reml;
  class USUBJID AVISTPT;
  model  $\Delta$ QTcF=PRTAN CONC1 AVISTPT CBASE / solution cl noint alpha=0.1
    alphap=0.1 covb ddfm=kr;
  random int CONC1 / type=un subject=USUBJID s;
run;
```

Throughout the LME modelling, for any timepoints where triplicate values are collected for QTcF, then the arithmetic average of the triplicates should be analysed.

QMD Ref: Worldwide-TMP-ST-054-1.0_Effective: 12Aug2022	Governing QMD: Worldwide-SOP-ST-026
Confidentiality Statement	
This document is the property of Worldwide Clinical Trials Inc. and may not be duplicated, copied, altered or removed from company without prior approval from Worldwide Quality Assurance or in compliance with Worldwide Standard Operating Procedures.	

Worldwide Clinical Trials Controlled Quality Management Document		
 WORLDWIDE CLINICAL TRIALS	Sponsor:	Eli Lilly and Company
	Protocol Number:	J4N-MC-YFAA
STATISTICAL ANALYSIS PLAN		

A scatter plot of QTcF data vs LY3885125 plasma PK concentration will also be presented for all timepoints where an ECG and PK sample were drawn within the same 10 minute window, with unique formatting for each treatment group.

All ECG data, including details of any abnormalities, will be listed.

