#### 4.1.1. Part A - Single Ascending Dose (SAD) Cohorts 1-6 (Cohort 6 optional)

Part A will consist of up to 6 single-dose levels, Cohorts 1 to 6, with the following numbers of participants randomized to LY3885125 or placebo as follows and also summarized in Table 4.1:

- Cohorts 1 and 2: a total of [REDACTED] participants ([REDACTED] per cohort) randomized 6:2 to LY3885125:placebo.
- Cohorts 3 through 5: total of [REDACTED] participants ([REDACTED] per cohort) randomized 9:2 to LY3885125:placebo.
- Cohort 6 (optional): total of [REDACTED] participants randomized 10:9 to LY3885125:placebo. This cohort will consist of participants with dyslipidemia on a stable moderate or high -intensity dose of statin; CCI [REDACTED]

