#### **9.5. Sample Size Determination**

Enrollment for Part A will enable completion of approximately 68 participants in up to 6 cohorts. Enrollment of 19 participants, randomized 10:9 to LY3885125:placebo in Cohort 6 was

CCI [REDACTED]

Enrollment for Part B will enable completion of approximately 44 participants in a single cohort that consists of 3 treatment arms with 2 doses administered per arm. The sample size for Part B was CCI [REDACTED]

Participants may be replaced at the discretion of the sponsor for adequate evaluation of study endpoints.

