### 5.2.2 Baseline

In Part A, baseline is defined as the last non-missing value (either scheduled, unscheduled or repeat) before the participant receives the first dose of study drug.

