	14.3.1.5	Treatment Emergent Adverse Events Leading to Early Termination by System Organ Class and Preferred Term, Part A – Safety Analysis Set	IP	14.3.1.2
	13.3.1.6	Treatment Emergent Adverse Events by System Organ Class, Preferred Term and Maximum Severity, Part A – Safety Analysis Set	IP	-
	14.3.1.7	Treatment Emergent Adverse Events by System Organ Class, Preferred Term and Strongest Relationship, Part A – Safety Analysis Set	IP	-
14.3.2	Other Adverse Events			
	14.3.2.1	Listing of Deaths – Full Analysis Set	IP	(Listing) 16.2.7.1
	14.3.2.2	Listing of Serious Adverse Events – Full Analysis Set	IP	-
	14.3.2.3	Listing of Abnormal Laboratory Values – Safety Analysis Set	IP	-
14.3.4	Other			
	14.3.4.1	Vital Signs, Descriptive Statistics for Observed Values and Change from Baseline, Part A – Safety Analysis Set	IP	-
	14.3.4.3.1	Hematology Data, Descriptive Statistics for Observed Values and Change from Baseline, Part A – Safety Analysis Set	IP	-
	14.3.4.3.2	Hematology Data, Normal Range Shifts, Part A – Safety Analysis Set	IP	-
	14.3.4.4.1	Serum Chemistry Data, Descriptive Statistics for Observed Values and Change from Baseline, Part A – Safety Analysis Set	IP	14.3.4.3.1
	14.3.4.4.2	Serum Chemistry Data, Normal Range Shifts, Part A – Safety Analysis Set	IP	14.3.4.3.2
	14.3.4.5.1	Urinalysis Data, Descriptive Statistics for Observed Values and Change from Baseline, Part A – Safety Analysis Set	IP	-

QMD Ref: Worldwide-TMP-ST-054-1.0_Effective: 12Aug2022	Governing QMD: Worldwide-SOP-ST-026
Confidentiality Statement This document is the property of Worldwide Clinical Trials Inc. and may not be duplicated, copied, altered or removed from company without prior approval from Worldwide Quality Assurance or in compliance with Worldwide Standard Operating Procedures.	

Worldwide Clinical Trials Controlled Quality Management Document		
 WORLDWIDE CLINICAL TRIALS	Sponsor:	Eli Lilly and Company
	Protocol Number:	J4N-MC-YFAA
STATISTICAL ANALYSIS PLAN		

Section Number	Table Number	Table Title	Validation Method	Shell Number (if repeat)
	14.3.4.5.2	Urinalysis Data, Normal Range Shifts, Part A – Safety Analysis Set	IP	-
	14.3.4.6.1	Safety ECG Data, Descriptive Statistics for Observed Values and Change from Baseline, Part A – Safety Analysis Set	IP	-
	14.3.4.6.2	Safety ECG Data, Descriptive Statistics for QTcF Thresholds, Part A – Safety Analysis Set	IP	-

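### The QTcF threshold table counts post-dose exceedances without regard to baseline, so it cannot separate pre-existing from post-dose exceedance; in practice this affects the >450 ms row

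*SAP*

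**What the plan says.** SAP 5.11.6 plans the number and percentage of participants in five QTcF categories. Three are absolute and take the largest value after dosing: "Largest postdose assessment of QTcF > 450", then the same for 480 and 500. Two are changes, starting with "Largest QTcF change from baseline > 30" and then 60. The output is Table 14.3.4.6.2, titled "Safety ECG Data, Descriptive Statistics for QTcF Thresholds"; the title adds no baseline condition.

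A baseline exists in the plan. SAP 5.2.2 says "baseline is defined as the last non-missing value (either scheduled, unscheduled or repeat) before the participant receives the first dose of study drug". Within this table only the two change categories use it. No row gives the number above each cut-off before dosing.

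Under SAP 5.3 results are shown by dose, with pooled active and pooled placebo columns. The ECG shift table in SAP 5.11.6 and section 10 uses the overall interpretation (normal, abnormal not clinically significant, abnormal clinically significant), not QTcF category.

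**The concern.** In an outlier table for a first-in-human study, a reader wants to know who crossed a threshold after dosing. As defined, the >450 row mixes two kinds of participant: those who crossed it after dosing and those who were above it beforehand. A participant who goes from 460 ms at baseline to a post-dose maximum of 455 ms has fallen, yet enters the >450 row of the assigned dose.

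The change rows do not resolve this, because they are separate counts and are not crossed with the absolute rows. With 6 or 9 people per dose, one such case could make an apparent step between dose levels, or blur a real one.

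**Working it through.** **1. Column sizes.** Protocol 4.1.1 has Cohorts 1-2 "per cohort) randomized 6:2 to LY3885125:placebo" and Cohorts 3-5 "per cohort) randomized 9:2 to LY3885125:placebo". Protocol 9.5 adds "Enrollment of 19 participants, randomized 10:9 to LY3885125:placebo in Cohort 6 was" and states "Enrollment for Part A will enable completion of approximately 68 participants in up to 6 cohorts". Reading the ratios as counts:

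2 × (6+2) + 3 × (9+2) + (10+9) = 16 + 33 + 19 = 68.

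This reproduces the protocol's figure. (The figure of 30 that appears for Cohorts 1 and 2 in SAP section 4 fits neither 6:2 nor 68, and is treated here as a text-reading artefact.) SAP sections 1 and 3 say that only Cohorts 1-5 were run. That gives 2×6 + 3×9 = 39 active and 5×2 = 10 placebo participants.

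**2. Weight of one person.** 1/6 = 16.7%; 1/9 = 11.1%; pooled active 1/39 = 2.6%; pooled placebo 1/10 = 10.0%.

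**3. How the rule classifies** (illustrative values, ms):

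| Baseline | Largest post-dose | Counted >450 as planned | At or below 450 at baseline, above after | Change >30 |
|---|---|---|---|---|
| 460 | 455 | yes | no | no |
| 455 | 458 | yes | no | no |
| 440 | 458 | yes | yes | no |
| 415 | 458 | yes | yes | yes |

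The first three rows look identical in the planned table.

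**4. How often.** The documents give no QTcF distribution. Assumed: true QTcF mean 415 to 425 ms, between-participant SD 18, baseline error SD 5, post-dose time-point SD 7, 8 to 12 post-dose time points, no drug effect, no entry limit. Observed baseline SD = √(18² + 5²) = 18.68. The chance p that one baseline exceeds cut-off c is the upper normal tail at (c − mean)/18.68, and the chance of at least one such person among n is 1 − (1 − p)^n.

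| Cut-off | p (mean 415 to 425) | n = 6 | n = 9 |
|---|---|---|---|
| 450 | 3.05% to 9.04% | 17% to 43% | 24% to 57% |
| 480 | 0.025% to 0.16% | 0.2% to 1.0% | 0.2% to 1.5% |
| 500 | at most 0.003% | at most 0.02% | at most 0.03% |

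With a lower mean of 405 to 410 ms, p for 450 is 0.8% to 1.6%, and the chance for n = 9 is 7% to 14%.

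**5. Share of the >450 count.** By simulation (400,000 participants per setting), 96% to 99% of those with baseline above 450 also have a post-dose maximum above 450. The overall chance of a maximum above 450 is 0.088 to 0.100 (mean 415) and 0.21 to 0.23 (mean 425). The share from pre-existing cases runs from 0.0305 × 0.981 / 0.100 = 0.30 (mean 415, 12 time points) to 0.0904 × 0.973 / 0.207 = 0.42 (mean 425, 8 time points). At most about 0.1% of these cases also show a change above 30 ms.

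**6. What remains after a baseline condition.** Among participants at or below 450 at baseline, the chance of a post-dose maximum above 450 with no drug effect is (0.088 − 0.0305 × 0.965) / 0.9695 = 6% at the low end and (0.230 − 0.0904 × 0.988) / 0.9096 = 15% at the high end. In a 9-person column that is up to 9 × 0.06 = 0.5 to 9 × 0.15 = 1.4 people by chance alone.

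**7. If entry QTcF were capped.** With an assumed limit of 450 ms on a single screening reading (error SD 7), p falls to 1.1% to 2.9%, the chance for n = 9 to about 10% to 23%, and the share of the >450 count to 15% to 21%.

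**The case against.** The strongest reply is that baseline is already handled in several places. The same table has the >30 and >60 ms change rows. SAP 5.11.6 also plans change-from-baseline summaries and a concentration-QTc model of the change in QTcF with baseline as covariate. Every ECG is listed, and with 49 participants any flagged person can be looked up. This stands as mitigation, but it leaves the threshold table unable to make the distinction itself.

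Second, the frequency rests on assumptions. Protocol section 5 uses the screening ECG for eligibility, and exclusion criteria 13, 19 and 20 in Protocol 5.2 are fully redacted, so an entry limit may exist. This stands: it would cut the frequency substantially. It would not remove the issue, since baseline is a later reading than screening. The table shells are not in the documents either, and may carry a baseline row or footnote.

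Third, absolute counts have a purpose of their own. The individual QTcF criterion in Protocol 7.1.2 is an absolute 500 ms with no baseline condition, and the >500 row mirrors it. This stands, and is a reason to keep the planned counts.

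Fourth, a baseline condition does not isolate a drug effect. Step 6 shows 6% to 15% still flagged by chance, so a label such as new onset would claim too much. This stands and shapes the fix.

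A reader might also infer a bias from most such people falling in active columns. That does not follow: 39 of 49 participants are active, the table gives percentages, and placebo is counted by the same rule.

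**Conclusion.** The point holds as a gap in presentation. The absolute QTcF categories ignore baseline, no planned summary table crosses QTcF category with baseline, and in columns of 6 or 9 one pre-existing case shows as 16.7% or 11.1%.

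The practical effect is almost entirely in the >450 ms row. Under the stated assumptions the chance of a pre-existing case in a 9-person column is 24% to 57% for 450 ms, at most 1.5% for 480 ms and about 0.03% or less for 500 ms. The 450 ms figure falls to about 10% to 23% under a hypothetical screening limit, and to 7% to 14% with lower assumed means.

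A reader might infer that all three counts are contaminated, or that participants with long baselines were enrolled. The documents support neither: they show the rule, not the data. Safety analyses are descriptive (Protocol 9.3.5) and Part B will not proceed (SAP section 2), so no later dose step in this study depends on the table. This is a worthwhile low-cost improvement, not a flaw that invalidates the safety analysis.

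**What to change.** In SAP 5.11.6 and Table 14.3.4.6.2, keep the unconditional post-dose counts and the two change rows as planned. For each of the three cut-offs add:

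- (a) the number of participants above the cut-off at baseline, using the SAP 5.2.2 baseline with triplicates averaged as in SAP 5.2.7;
- (b) the number at or below the cut-off at baseline whose largest post-dose value is above it. The denominator is participants at or below the cut-off at baseline with at least one post-dose ECG. Footnote it, since SAP 5.3 otherwise uses the column N.

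Label (b) neutrally, for example *post-dose exceedance among those not exceeding at baseline*, and state that it is to be read against pooled placebo because a maximum over many time points exceeds a single baseline by chance. With 10 placebo participants that comparison is itself rough.

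Cost: a few lines of SAP text and six extra rows in one table, with no new data. The denominators in (b) are smaller and can differ between rows. SAP section 5 allows the change as an amendment before Part A database lock, or in an addendum after it.
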